8.4.5 REPORTING OF PREGNANCY

If a pregnancy occurs in a female subject enrolled into the study, or a female partner of a male subject within 30 days of completing the CPX-351 infusion, the pregnancy must be reported to the key sponsor contact. Information regarding the pregnancy and/or the outcome may be requested by the key sponsor.

In addition to reporting any pregnancies occurring during the study, investigators will monitor for pregnancies that occur after the last dose of CPX-351 through 3 months for female subjects and for 6 months for the female partner of the male subjects.

The pregnancy should be reported to the key sponsor contact within 24 hours of the investigators knowledge of the pregnancy event.

If a lactation case occurs while the female subject is taking protocol required therapies report the lactation case to the key sponsor contact.

In addition to reporting a lactation case during the study, investigators should monitor for lactation cases that occur after the last dose of protocol required therapies through 3 months.

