5 STUDY ENROLLMENT AND WITHDRAWAL

5.1 PARTICIPANT INCLUSION CRITERIA

Patients must meet all of the following criteria to be eligible for study entry:

1. Be willing and able to provide written informed consent/assent for the trial.
2. Be ≥ 18 years of age on day of signing informed consent.
3. Able to adhere to the study visit schedule and other protocol requirements.
4. Pathologically confirmed B- or T-cell acute lymphoblastic or mixed phenotype acute leukemia, with $\geq 5\%$ peripheral blood or bone marrow lymphoblasts and/or extramedullary disease $>1 \times 1 \text{ cm}$.
5. Relapsed or refractory acute lymphoblastic leukemia after at least 1 prior cycle of therapy. Patients with Philadelphia chromosome positive disease must have failed at least two prior tyrosine kinase inhibitors.
6. Eastern Cooperative Oncology Group (ECOG) performance status 0-1.
7. Cardiac ejection fraction $\geq 50\%$ by echocardiography or MUGA.
8. Must be at least 2 weeks out from any prior systemic chemotherapy, blinatumumab, radiation, and/or other investigational agents, and have recovered to grade 1 from any toxicity related to prior therapy. Glucocorticoids are permitted up to 1 day prior to the first dose.
9. Serum bilirubin and creatinine $\leq 1.5 \times$ upper limit of normal (ULN). AST and ALT must be $\leq 3 \times$ ULN, unless there is suspected liver involvement.
10. Females of childbearing potential (FCBP) must have a negative serum pregnancy test at screening. A FCBP is considered when a sexually mature female: 1) has not undergone a hysterectomy or bilateral oophorectomy; or 2) has not been naturally postmenopausal for at least 12 consecutive months.
11. A FCBP must agree to use of two methods of highly effective contraception, be surgically sterile, or abstain from heterosexual activity for the course of the study through 30 days after the last dose of study treatment.
12. Male subjects must agree to use an adequate method of contraception starting with the first dose of study therapy through 30 days after the last dose of study therapy. Men must agree to not donate sperm during and after the study

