5.2 PARTICIPANT EXCLUSION CRITERIA

Any of the following is a criterion for exclusion from the study:

1. Clinical evidence of active central nervous system (CNS) leukemia.
2. Any major surgery or radiation therapy within four weeks.
3. Any active infection requiring systemic therapy, including HIV, Hepatitis B, and/or Hepatitis C.
4. Has a history or current evidence of any condition, therapy, or laboratory abnormality that might confound the results of the trial, interfere with the subject's participation for the full duration of the trial, or is not in the best interest of the subject to participate, in the opinion of the treating investigator (including but not limited to severe graft-versus-host disease, unstable angina, pulmonary hypertension, active/prior veno-occlusive disease of the liver, or severe CHF (NYHA III-IV).
5. Patients with active (uncontrolled, metastatic) second malignancies are excluded.
6. Is pregnant or breastfeeding, or expecting to conceive or father children within the projected duration of the trial, starting with the screening visit through 30 after the last dose of trial treatment.
7. Hypersensitivity to cytarabine, daunorubicin, or liposomal products.
8. History of Wilson's disease or other copper-metabolism disorder.
9. Patients with prior cumulative anthracycline exposure of greater than 368 mg/m² daunorubicin (or equivalent).

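### Contraception and the no-conception condition stop 30 days after the last dose, while section 8.4.5 looks for pregnancies to 3 months (women) and 6 months (partners of men), with no explanation

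*Combined protocol and SAP*

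**What the plan says.** Section 5.1, inclusion 11, asks women of childbearing potential to use two highly effective methods, be surgically sterile, or "abstain from heterosexual activity for the course of the study through 30 days after the last dose of study treatment". Inclusion 12 asks men to use contraception "starting with the first dose of study therapy through 30 days after the last dose of study therapy" and adds: "Men must agree to not donate sperm during and after the study". That last condition has no end date.

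Section 5.2, exclusion 6, excludes anyone pregnant, breastfeeding, or planning to conceive or father a child, "starting with the screening visit through 30 after the last dose of trial treatment". No unit follows the 30.

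Section 8.4.5 sets four further rules:

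- Its opening sentence makes reporting mandatory for a pregnancy in an enrolled woman or in "a female partner of a male subject within 30 days of completing the CPX-351 infusion, the pregnancy must be reported".
- Its second paragraph says that "investigators will monitor for pregnancies that occur after the last dose of CPX-351 through 3 months for female subjects and for 6 months", the latter period applying to partners of men in the trial.
- It then gives a time limit for the report: "The pregnancy should be reported to the key sponsor contact within 24 hours of the investigators knowledge of the pregnancy event".
- For breastfeeding, "investigators should monitor for lactation cases that occur after the last dose of protocol required therapies through 3 months".

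**The concern.** The protocol gives pregnancy surveillance its own, sex-specific windows of 3 and 6 months after the last dose. That choice implies that a pregnancy arising in that time is worth knowing about. Yet the eligibility criteria release both sexes from contraception, and from the undertaking not to conceive, at day 30. For men the contrast is sharper, because the sperm-donation condition continues past the point where contraception stops. No section reconciles these periods.

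What is at stake is participant protection on a small scale. The drug combines two cytotoxic agents, and the trial is open to adults from age 18. As the criteria are written, someone could stop contraception on day 30 in full compliance, while the protocol still counts a later conception as an event to look for.

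**Working it through.** The plan gives no figure to reproduce, so the check sets the time windows side by side and subtracts.

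| Rule | Applies to | Ends |
|---|---|---|
| Inclusion 11, contraception | women of childbearing potential | 30 days after last dose |
| Inclusion 12, contraception | men | 30 days after last dose |
| Inclusion 12, sperm donation | men | no end date |
| Exclusion 6, no conception | both sexes | 30 after last dose, unit missing |
| 8.4.5, pregnancy monitoring | women | 3 months after last dose |
| 8.4.5, pregnancy monitoring | partners of men | 6 months after last dose |
| 8.4.5, lactation monitoring | women | 3 months after last dose |
| 8.4.5, mandatory report | partners; possibly women too | 30 days after completing the infusion |
| 8.4.5, 24-hour report | not limited | no end date |

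**Unit in exclusion 6.** Inclusion 11 and 12 both use 30 days from the same starting point, so days is the evident reading.

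**Length of the gap.** Taking a month as 365/12 = 30.42 days (an assumption, since the protocol does not define a month):

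- 3 months = 3 × 30.42 = about 91 days; 6 months = 6 × 30.42 = about 183 days.
- Women: 91 − 30 = about 61 days, or about 2 months.
- Men and partners: 183 − 30 = about 153 days, or about 5 months.

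**Example.** A participant given induction only has the last dose on study day 5 (section 6.1.7).

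- Contraception ends on day 5 + 30 = 35.
- Monitoring ends on about day 5 + 91 = 96 for a woman.
- Monitoring ends on about day 5 + 183 = 188 for a man's partner.

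Consolidation moves all these dates later but leaves the gaps unchanged, because contraception and monitoring both run from the last dose.

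**Reporting sentence.** The 30-day limit in the opening sentence of 8.4.5 can be read in two ways.

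- If it covers both groups, it is shorter than both monitoring windows.
- If it belongs only to the partner clause, it is shorter than the 6-month partner window, and an enrolled woman's pregnancy is reportable with no stated limit.

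On either reading the partner limit does not match the partner monitoring period. Its clock is also worded differently, running from completion of the infusion and not from the last dose. The 24-hour sentence comes after the monitoring sentence, carries no end date, and most naturally covers pregnancies found in the longer windows.

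**The case against.** The strongest reply is that contraception and surveillance serve different purposes. A sponsor may reasonably watch for outcomes beyond the period in which it requires protection. That stands: a reader might infer that the protocol contradicts itself, and it does not.

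A second reply is that nothing in the documents shows 30 days to be too short. That also stands. A reader might infer from the 3- and 6-month windows that the risk lasts that long, but the protocol never states its duration. The case is for alignment, using the only longer figures that the protocol supplies. If the sponsor has a basis for 30 days, one sentence giving it would answer most of the point, though exclusion 6 would still need its unit.

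Third, the open-ended sperm-donation condition may simply be a stricter precaution for third parties. That is fair. It shows that the precautions for men have different lengths, not that 30 days is wrong.

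Fourth, a reader might infer from the opening sentence of 8.4.5 that pregnancies after day 30 go unreported. The section does not support this. Its second paragraph refers to reporting any pregnancy during the study, without the 30-day limit, and the 24-hour sentence then follows the monitoring windows. Sections 5.4.2 and 10.4.3 also provide for continued contact with people who leave early and for 3-monthly safety assessment of those who have not gone on to transplant or other therapy. What remains is loose wording.

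Finally, participants take their instructions from the consent form, which is not available here. What they are actually told about contraception cannot be judged, so the finding concerns the protocol text only.

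**Conclusion.** The point holds as an unexplained mismatch between reproductive-safety windows. Protection ends about 61 days before surveillance does for women, and about 153 days before for men and their partners. These are calendar gaps, not risks. They rest on reading the 30 in exclusion 6 as days and on a month of about 30.4 days.

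The rules apply to a planned 10 participants, or 19 if the trial is expanded (section 10.4.1). A reader might try to work out how many participants a change would still reach by subtracting the 7 already treated (section 2.3.2). The documents do not support such a count. They do not say that those 7 are trial participants, section 10.5 targets evaluable patients, and sections 5.4.2 and 10.6.1 allow replacement.

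No endpoint, analysis, sample size or decision rule is affected. The change is worth making because it costs little and concerns participant protection, not because the current text is shown to be unsafe.

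**What to change.** **Main change, sections 5.1 and 5.2.**

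- Extend inclusion 11 and the female part of exclusion 6 to at least 3 months after the last dose of CPX-351.
- Extend inclusion 12 and the male part of exclusion 6 to at least 6 months after the last dose.
- Write out the time unit in exclusion 6.

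**Optional wording, section 8.4.5.**

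- Replace the 30-day limit on partner pregnancies with 6 months after the last dose.
- Leave the clause on pregnancy in an enrolled woman without a new cap. A 3-month limit there would narrow a duty that, on one reading, now has no end date.
- State that the 24-hour report covers every pregnancy found in the monitoring windows.

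**Cost.** This is a wording amendment to three eligibility criteria, with matching consent text and, if adopted, the edits to 8.4.5. Section 13.2 already requires IRB review of amendments and a decision on re-consent. No visit, test or sample is added. The downside for participants is about 2 more months of contraception for women and about 5 for men.

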8.5 STUDY HALTING RULES

Safety assessments will consist of monitoring and recording all adverse events and serious adverse events, the regular monitoring of hematology and blood chemistry parameters and regular physical examinations. Adverse events will be evaluated continuously throughout the study. Safety and tolerability will be assessed according to the NIH/NCI Common Terminology Criteria for Adverse Events version (CTCAE v5.0) that is available at: <http://evs.nci.nih.gov/ftp1/CTCAE/About.html>

The Protocol Monitoring Committee (PMC) at Moffitt monitors its assigned ongoing research protocols for: adverse event reporting, data and safety monitoring, and internal audit findings. The PMC, upon review of any agenda item, may approve the study for continuation, require revisions, suspend or close a protocol. The PMC meets monthly and reviews accrual, patterns and frequencies of all adverse events, protocol violations and when applicable, internal audit results.

Investigators of studies which are designated to be reviewed by the PMC for data and safety monitoring, shall provide a statistical report of the study's progress and summary of adverse events and deviations based on the phase of the study and the associated risk of the study or more often if applicable. The PI will be notified for recommendations or notifications after the PMC review in regards of continuation or stopping the clinical trial.

8.6 SAFETY OVERSIGHT

Serious Adverse Events: Serious Adverse Events (SAEs) from this protocol will be reported concurrently to the IRB (per IRB guidelines) and Jazz Pharmaceuticals, Inc. within 24 hours of staff awareness of the event. The Protocol Monitoring Committee (PMC) will review these SAEs in accordance with their policy. The data and safety plan will define dose limiting toxicities and criteria for stopping the trial according to rules set forth by this protocol. This trial will be continuously monitored by the PI and the research team. A final safety and monitoring report will be submitted to the PMC. This protocol will be subject to periodic internal audits based on risk or as recommended by the PMC.

9 CLINICAL MONITORING

Data will be captured in OnCore, Moffitt's electronic Clinical Trials Database. For each participant enrolled, the electronic CRF must be completed by the assigned data manager or other authorized study staff. Any paper forms should be typed or filled out indelible ink and must be legible. Errors should be crossed out but not obliterated, the correction inserted, and the change initialed and dated by the investigator or his/her authorized delegate. This also applies to records for those patients who fail to complete the study. If a patient stops dosing or terminates from the study, the dates and reasons must be noted on the CRF. If a patient terminates from the study because of a DLT, thorough efforts should be made to clearly document the outcome.

Regulatory documents and case report forms will be monitored internally according to Moffitt Cancer Center Monitoring Policies. Monitoring will be performed regularly by the MCC Clinical Monitoring

Core for accuracy, completeness, and source verification of data entry, validation of appropriate informed consent process, reporting of SAEs, adherence to the protocol, Good Clinical Practice (GCP) guidelines, and applicable regulatory requirements.

10 STATISTICAL CONSIDERATIONS

10.1 STATISTICAL AND ANALYTICAL PLANS

The following study is a phase 2 pilot trial. Exploratory analyses of remission rate, safety, progression free survival, and overall survival are planned.

10.2 STATISTICAL HYPOTHESES

- All Endpoints are exploratory, and may be used to facilitate design of an expansion or subsequent phase 2 study.
- Primary Efficacy Endpoint:
 - Complete Remission and Complete Remission with incomplete hematologic recovery will serve as the primary endpoint.
- Secondary Efficacy Endpoint(s):
 - Safety
 - Minimal Residual Disease Remission Rate
 - Progression Free Survival
 - Overall Survival

10.3 ANALYSIS DATASETS

- All patients receiving at least one dose of CPX-351 will be evaluable for safety.
- Efficacy analyses will be restricted to those receiving a full cycle of induction therapy.

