3 OBJECTIVES AND PURPOSE

Primary Objective:

To estimate the complete response rate following treatment with CPX-351. Complete remission will be evaluated by bone marrow biopsy at day 28 of therapy in all patients with medullary disease receiving at least one full cycle of CPX-351. For patients with extramedullary disease, CT or PET/CT will be used for response. Cheson criteria (2003) will be used to evaluate remission status, specifically complete remission (CR), complete remission with incomplete hematologic recovery (CRi/CRh), partial response (PR), and aplasia.

Important Secondary Objectives:

Additional clinical endpoints will include

- 1) To evaluate safety and tolerability of CPX-351 using CTCAE 5.0.
- 2) Minimal residual disease assessment (MRD) by 10 color flow cytometry and next generation sequencing (NGS) by Clonoseq (for Philadelphia negative leukemia) or PCR for BCR-ABL (for Philadelphia positive leukemia).
- 3) Progression Free Survival as defined by Cheson Criteria, namely progression, failure to respond, or death, as assessed from time of first treatment.
- 4) Overall Survival as defined by Cheson Criteria, namely death due to any cause as assessed from time of first treatment.

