5.4.2 HANDLING OF PARTICIPANT WITHDRAWALS OR TERMINATION

Every effort will be made to maintain contact with a subject who withdraws early. If the subject remains at MCC for further care, clinic visits may be tracked and the condition of the subject followed. If the subject is not continuing care at MCC, contact information will be updated at the end of treatment visit, including accurate phone numbers, and email address. The importance of the follow-up period for AEs and SAEs will be stressed to the subject.

All subjects receiving at least 1 day of therapy will be evaluable for safety. Replacement of participants is permitted for those who screen fail or drop out prior to completing initial response assessment at day 28 of treatment, in order to meet the accrual goal of this study.

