6.1.9 DURATION OF THERAPY

All patients completing induction will be evaluable for efficacy. Consolidation may be started at the time of hematologic recovery (28-75 days after start of induction) for those achieving a complete remission or complete remission with incomplete hematologic recovery. Consolidation cycles may be repeated at the time of hematologic recovery for a maximum total of 3 consolidation cycles.

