10.4 DESCRIPTION OF STATISTICAL METHODS

10.4.1 GENERAL APPROACH

This will be a phase 2 pilot trial to assess efficacy of CPX-351 in relapsed and refractory acute lymphoblastic leukemia. If 4 or more CR/CRi are observed in the first 10 patients, Jazz Pharmaceuticals will consider an increase in the budget to facilitate accrual to a total of 19 patients (ie, 9 additional subjects), possibly in a multi-center setting. This would be sufficient to test our hypothesis that CPX-351 will increase the CR/CRi rate from a historical standard of 35% to 65% (as summarized in section 2.2) using a power of 90% and type I error rate of 0.1.

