10.5 SAMPLE SIZE

Moffitt is a high volume center for ALL, with approximately 50 new cases referred to our center yearly, of whom ~10% are anticipated to be refractory to therapy, and ~50% will relapse within 2 years of therapy. The current inclusion and exclusion criteria developed within this protocol, as well as prior enrollment to protocols targeting ALL, support a screen failure rate of less than 10%. Similarly, internal experience with CPX-351 supports a drop-out rate (ie, failure to complete induction) of less than 10%. Accordingly, we anticipate full accrual of 10 evaluable patients within 24 months.

As previously noted, this is a phase 2 pilot study designed to assess the feasibility and provide a preliminary assessment of safety and efficacy to support a more formal phase 2 study.

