10.6 MEASURES TO MINIMIZE BIAS

10.6.1 ENROLLMENT

Patients with relapsed ALL will be enrolled from the Malignant Hematology clinic at the Moffitt Cancer Center. Patients will not be blinded to therapy. Given the exploratory nature of this study, stratification of patients will not be performed. Patients who are unable to complete a full course of induction may be replaced to facilitate assessment of overall remission rate.

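### The primary remission rate counts only patients given a full induction cycle; dosed non-completers may be replaced and are nowhere scored as non-responders

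*Combined protocol and SAP*

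**What the plan says.** Section 10.3 defines two analysis sets. Safety takes every patient with at least one dose of CPX-351. For efficacy, "Efficacy analyses will be restricted to those receiving a full cycle of induction therapy". Section 3 has the same limit in the primary objective, where marrow remission is evaluated "in all patients with medullary disease receiving at least one full cycle of CPX-351". Section 6.1.9 adds "All patients completing induction will be evaluable for efficacy", which admits completers but does not itself exclude anyone.

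Two passages deal with replacement, and they differ:

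- Section 5.4.2: "Replacement of participants is permitted for those who screen fail or drop out prior to completing initial response assessment at day 28 of treatment".
- Section 10.6.1: "Patients who are unable to complete a full course of induction may be replaced to facilitate assessment of overall remission rate".

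Both are permissive, and neither excepts any reason for the loss.

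Section 10.5 equates drop-out with failure to complete induction, puts it below 10%, and concludes "we anticipate full accrual of 10 evaluable patients within 24 months". The expansion rule in Section 10.4.1 begins "If 4 or more CR/CRi are observed in the first 10 patients", and Section 10.4.2 words it on the first ten patients treated. Section 10.2 calls all endpoints exploratory, and Section 10.4.2 gives its Simon two-stage table for illustration only.

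**The concern.** Whether a patient belongs to the efficacy set depends on what happens after dosing starts. A patient who cannot finish induction because of toxicity, early death or progression has not benefited, yet the plan leaves that patient out of the primary rate and lets another take the place. No section scores a dosed non-completer as a non-responder, keeps a replaced patient in the denominator, or plans to report CR/CRi in all treated patients. The persistent-disease category in Appendix A does not close the gap. It covers only patients who survive at least 7 days after completing initial treatment and have evidence of leukemia.

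Estimating this rate is the primary objective. It will be read against the 35% benchmark of Section 2.2, and it is the evidence for expansion. The documents also do not connect the expansion rule, worded on treated patients, with the full-cycle set, the target of 10 evaluable patients and the replacement rules.

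**Working it through.** **Who is affected.** Section 6.1.7 gives induction as three doses, on days 1, 3 and 5. Full cycle is not defined further. On the natural reading, Section 10.3 excludes patients who never receive one of the three doses; Section 6.1.8 lets a dose missed or delayed for toxicity be given later. Section 5.4.2 reaches further: a patient who receives all three doses but is lost before day 28 is evaluable under Section 6.1.9 and replaceable under Section 5.4.2. A completer with marrow disease and no marrow assessment cannot be CR or CRi under Appendix A. The gap therefore concerns dosed non-completers and the unclear effect of Section 5.4.2.

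**The plan's own figures.** Inputs from Sections 10.4.1 and 10.4.2: p0 = 0.35, p1 = 0.65; stop at 3 or fewer of 10; otherwise go to 19 and reject p0 at 10 or more. Exact binomial calculation gives a probability of early stopping at p0 of 0.514, an expected N of 10 + 0.486 × 9 = 14.38, alpha 0.0844 and power 0.9048 (beta 0.095). All agree with the printed table. The arithmetic is sound; the issue is the denominator.

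**Bias in the reported rate.** Let d be the share of dosed patients excluded and k their response rate relative to completers. With a true rate of 0.35 per dosed patient, the completer rate is pc = 0.35 / ((1 − d) + d·k). The values of d bracket the plan's expectation of less than 10%; k is an assumption.

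| k | d | pc | P(4 or more of 10) | Two-stage alpha |
|---|---|---|---|---|
| 1 (equal response) | any | 0.350 | 0.486 | 0.084 |
| 0.5 | 0.05 | 0.359 | 0.510 | 0.098 |
| 0.5 | 0.10 | 0.368 | 0.536 | 0.114 |
| 0 (never respond) | 0.05 | 0.368 | 0.536 | 0.114 |
| 0 | 0.10 | 0.389 | 0.589 | 0.155 |

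The last two columns apply only if the 4-of-10 rule is run on completers after replacement. If it is run on the first 10 dosed patients, the chance of passing stays at 0.486. At k = 0 the two readings differ by 0.536 − 0.486 = 0.050 or 0.589 − 0.486 = 0.103.

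**Likelihood of an exclusion.** The chance of at least one before 10 completers accrue is 1 − (1 − d)^10, which is 0.40 at d = 0.05 and 0.65 at d = 0.10. The chance of at least two is 1 − (1 − d)^10 × (1 + 10d), which is 0.10 and 0.30.

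**Example.** Four responders among 10 completers read as 40.0%. With one replaced dosed non-responder kept, the rate is 4/11 = 36.4%; with two, 4/12 = 33.3%, which is under 35%.

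**If 65% is a completer rate.** The all-dosed rate is 0.65 × ((1 − d) + d·k), and the table's design applied to all dosed patients gives, against baselines of 0.974 and 0.905:

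| k | d | All-dosed rate | P(4 or more of 10) | Power |
|---|---|---|---|---|
| 0.5 | 0.05 | 0.634 | 0.966 | 0.877 |
| 0.5 | 0.10 | 0.618 | 0.957 | 0.844 |
| 0 | 0.05 | 0.618 | 0.957 | 0.844 |
| 0 | 0.10 | 0.585 | 0.933 | 0.764 |

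**The case against.** This is an exploratory pilot of 10 patients, and its two-stage table is illustrative, so no confirmatory error rate is at risk. The expansion rule is already worded on treated patients; on that reading the chance of expansion is not inflated, and the raised alpha figures belong to a reading the text does not favour. Those points stand.

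The bias is also small against the sampling error. At 10% exclusion with no responses among those excluded it is 38.9 − 35.0 = 3.9 percentage points, and 1.8 points at half the completer rate, whereas the exact 95% interval for 4/10 runs from 12.2% to 73.8%. The 4/12 example implies a loss of 2/12 = 16.7%, above the plan's expectation. That too is correct.

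Death and progression are not named as grounds for replacement; the text simply excepts no reason. Induction is three inpatient doses over five days, and missed doses may be given later, so few patients should fall out on the three-dose reading.

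These points limit the size of the problem but do not remove it. Section 10.3 is an explicit restriction, not a missing detail, and the reported rate is exposed to the bias whichever patients the expansion rule counts. Wide sampling error is no reason to keep a bias of known direction that a change of wording removes.

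**Conclusion.** The concern holds and should be fixed. Followed as written, the plan overstates the primary CR/CRi rate whenever dosed non-completers respond less often than completers. With a true rate of 35% per dosed patient and 5% to 10% excluded, the overstatement is about 1 to 4 percentage points across the half-rate and never-respond cases, and zero if excluded patients respond equally often. The chance of meeting the expansion rule rises, by up to 10.3 points, only if that rule is applied to completers after replacement. The exclusion shares and relative response rates are assumptions; the documents give only the expectation of less than 10% drop-out. The consequence is a modestly favourable estimate feeding the expansion decision, not a breached error rate.

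**What to change.** - Make all patients with at least one dose of CPX-351, already the safety set, the primary efficacy set.
- Score every dosed patient without a documented CR or CRi as a non-responder, including early deaths and patients who do not complete induction.
- State that replaced patients who were dosed stay in the denominator, and that the 4-of-10 rule uses the first 10 dosed patients, in line with Section 10.4.2.
- Keep the full-cycle analysis as supportive, and define full cycle.
- Align Sections 3, 5.4.2, 6.1.9, 10.3, 10.4.1, 10.4.2, 10.5 and 10.6.1.
- State whether 35% and 65% are rates per dosed patient or per completer.

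The cost is wording and a slightly less favourable reported rate; the pilot needs no extra patients. If 65% is a rate per dosed patient, there is no power cost. If it is a completer rate, power for the illustrative 19-patient design falls below the stated 90%, as the second table shows, and should be restated before any expansion. No treatment rule changes.
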